Patients will be approached in their second or third trimester regarding the study in the Obstetrics or Rehabilitation clinics if they have PGP. They will be given a flyer regarding the study. If interested in participating, they will either proceed to study visit 1 (baseline), if time permits, or set up a separate time for study visit 1 to take place. Patients will be consented and evaluated for eligibility at this baseline visit. Eligible patient will be randomized to either the control or intervention groups at study visit 1. They will receive the injected medication at study visit 1. This study will require study visits total, study visit 1 will be at the time of randomization,

study visit 2 will be 4 weeks after injection, study Visit 3 will be at 8 weeks after start of intervention/after injection. and study visit 4 will be 6 weeks post-delivery. There will be one follow-up phone call between visit 1 and 2 on day 7 following intervention to inquire about any medication side effects or adverse events. Study duration is 8 weeks per patient, with an expected two year total recruitment and data collection time period. At study visit 1, patients will be randomized to receive the intervention medication or active comparator and undergo a physical examination of the external musculoskeletal pelvis and will complete the NRS for 'worst pain' and 'mean pain' during the latest 48 hours, a pain diagram, a personal health information questionnaire regarding their pregnancy, past medical history, activity level and restrictions. Disability as measured by the Pelvic Girdle Questionnaire (PGQ) and Oswestry Disability Index (ODI), Health-Related Quality of Life (HRQL) measured by the Wellbeing NRS and work ability will be measured with one question from Workability Index i.e. "Current work ability compared with the lifetime best".

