3.5.2 Randomization

Randomization strategy will be developed in collaboration with Loyola Biostatistics Department, using blocks of 3 stratified on pain location and allocation will be a 1:1 ratio of patients in the intervention and control groups. The randomization procedure will take place at study visit 1 after informed consent is completed and eligibility status is determined. A research coordinator ([name]) blinded to the study will give precoded identical envelopes with randomization assignments to the patients at the conclusion of study visit 1. This assistant and an independent Data and Safety Monitoring Board (DSMB) will have access to the randomization code.

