3.8 Analysis

Data will be analyzed using descriptive univariate statistics with STATA 11.0. In this population, there is evidence from current literature that pain and disability may not be normally distributed. If this is the case, the primary and secondary outcomes, pain and disability respectively, will be presented as median values and interquartile ranges. Comparisons between the intervention groups at follow-up will be performed using the Mann Whitney U test and change within groups from baseline to follow-up will be examined using the Wilcoxon signed-rank test. If data are sufficiently normally distributed and differences are found, multivariate analyses will be conducted. This will determine the need to control for group differences based on location of pain, history of low back pain or pelvic girdle pain, age, educational level, parity, and time from pain onset. Additional secondary analyses will examine the impact of the treatment group assignment on physical examination tests using chi-square test of proportions.

4. Risks and Benefits

The excellent overall safety and efficacy record of injectable corticosteroids is well established²⁶. A prospective evaluation of intraarticular and periarticular injections with methylprednisolone found a very low rate of complications²⁷. Systemic effects of injectable corticosteroids are influenced by the agent used, dose, frequency and number of sites injected. Osteoporosis is found only with use of systemic/oral steroids and myopathy more commonly documented with oral fluorinated steroid use has not been reported with intraarticular injections. The ability of intraarticular injections to suppress the hypothalamic-pituitary-adrenal (HPA) axis

Protocol Version 4 – 03-06-2015

is well documented²⁸ but has not been described with extraarticular or ligamentous injections. A corticosteroid induced increase in glucose synthesis is not seen in soft-tissue injections of methylprednisolone acetate²⁹.

Fetal Risk and Benefit

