Appendix II: Sample Size Calculations

Sample size was determined under the assumption that a difference of 2 on NRS would have clinical relevance. This was based on the previous work of Elden¹⁴ in an RCT for acupuncture compared with sham for PGP in pregnancy. The 2 point difference on the NRS has also been used in other gynecologic RCTs in the measurement of pain.³³ The standard deviation of 25 mm was derived from the prior work of Bastiaenen¹⁶ in an RCT comparing a specific educational physical therapy program to usual care in postpartum PGP. No standard deviations were available in the Elden paper or in any other literature on this topic. For the primary outcome of patient pain ratings (0-10 NRS) after 4 weeks of physical therapy with or without methylprednisolone, a sample size of 50 (25 in each group) will give the study 80% power to identify a 2 point difference on the NRS (with [alpha] of .05). The 4 week follow-up time period is used because the clinical effect of the study medication is expected within the 4 weeks. An additional 5 participants in each group is added to account for a loss to follow-up of 10% which calculates to then 30 per treatment group. Power analyses were performed by using STATA

11.0. The basic formula for calculation is $\Delta/\sigma = 3.96/\sqrt{n}$, with Δ = effect size, σ = the standard deviation and n = number of patients needed.

Sensitivity analysis

Expected change in NRS (Effect size)	N if Power 80%	N if Power 90%
1	198 (99 per group)	264 (132 per group)
1.5	88 (44 per group)	118 (59 per group)
2	50 (25 per group)	66 (33 per group)
3	22 (11 per group)	30 (15 per group)

References:

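### Baseline NRS and the pain-location stratum are left out of the between-arm comparison of pain; one adjusted rank analysis fixed in advance would add modest precision and remove an undefined trigger

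*Combined protocol and SAP*

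**What the plan says.** Section 3.8 is the only place where the analysis is described. It warns that "there is evidence from current literature that pain and disability may not be normally distributed". In that case pain is summarised by medians and interquartile ranges, and "Comparisons between the intervention groups at follow-up will be performed using the Mann Whitney U test". Baseline values appear only in a within-group Wilcoxon signed-rank test of change.

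For the other case the section says: "If data are sufficiently normally distributed and differences are found, multivariate analyses will be conducted". It continues: "This will determine the need to control for group differences based on location of pain, history of low back pain or pelvic girdle pain", then "age, educational level, parity, and time from pain onset". Baseline NRS is not on that list. No between-arm test is named for normally distributed pain. If the Mann-Whitney sentence is instead read as covering both cases, the comparison is unadjusted in both.

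Elsewhere:
- Section 3 (Protocol): at visit 1 patients "will complete the NRS for 'worst pain' and 'mean pain' during the latest 48 hours", so two baseline pain scores exist.
- Section 3.5.2: allocation is made "using blocks of 3 stratified on pain location". The strata are not listed.
- Appendix II (sample size): the calculation is "For the primary outcome of patient pain ratings (0-10 NRS) after 4 weeks of physical therapy". Section 1.3 instead refers to a 2-point effect at both 4 and 8 weeks.

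**The concern.** There are two separate matters.

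The first is precision. A baseline measurement of the outcome and the stratification factor are usually the first candidates for adjustment. Both will be in hand for every randomized patient. The plan never uses the baseline score between arms. It uses the stratum only conditionally, and not at all in the non-normal case that it expects.

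The second is pre-specification. No normality criterion is given, and the plan does not say what the differences are differences in. They may be baseline imbalances between arms, as the following sentence suggests. They may also be differences in outcome, in which case adjustment would be chosen after seeing the result.

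In addition, the trial is sized on a 2-point difference, yet no between-arm estimate with a confidence interval is planned on that scale.

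**Working it through.** **Inputs from the documents.** Two-sided alpha 0.05 and 80% power (section 3.7); difference 2 points, SD 25 mm read as 2.5 points on the 0-10 scale, 25 per arm raised to 30 for a 10% loss (Appendix II); entry requires average NRS of at least 5 (section 3.1).

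**Assumptions.** The baseline to follow-up correlation r is not in the documents; 0 to 0.4 is shown. The entry rule restricts the baseline range and may lower r. Evaluable patients: 30 × 0.9 = 27 per arm.

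**Step 1, the plan's own figure.** Appendix II uses Δ/σ = 3.96/√n, so n = (3.96 × 2.5/2)² = 4.95² = 24.5, rounded up to 25 per arm. This reproduces. The formula has no baseline term.

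**Step 2, closed form at difference 2 and SD 2.5, 27 per arm.** Unadjusted: SE = 2.5 × √(2/27) = 0.680. ANCOVA multiplies this by √(1 − r²). Degrees of freedom are 52 unadjusted and 50 with baseline and a two-level stratum.

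| Analysis | Power | 95% CI half-width |
|---|---|---|
| Unadjusted t-test | 82.2% | 1.37 |
| ANCOVA, r = 0 | 82.2% | 1.37 |
| ANCOVA, r = 0.2 | 83.7% | 1.34 |
| ANCOVA, r = 0.3 | 85.6% | 1.30 |
| ANCOVA, r = 0.4 | 88.2% | 1.25 |

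**Step 3, simulation of the tests themselves.** 20,000 trials per scenario, 27 per arm, baseline an integer from 5 to 10, follow-up rounded and bounded to 0-10, two near-equal strata with no effect on pain. Rounding and bounding pull the realised difference to 1.85-1.93 and the SD to 2.15-2.38, so these powers are not at exactly 2 and 2.5. Rank ANCOVA regresses the ranked outcome on treatment, ranked baseline and stratum. Power in %:

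| Errors | Test | r = 0 | r = 0.2 | r = 0.3 | r = 0.4 |
|---|---|---|---|---|---|
| Normal | Mann-Whitney | 80.1 | 79.7 | 80.2 | 79.7 |
| | Rank ANCOVA | 79.3 | 80.4 | 82.6 | 85.3 |
| | ANCOVA | 80.8 | 81.8 | 84.1 | 86.7 |
| Moderate skew | Mann-Whitney | 86.2 | 85.1 | 84.7 | 83.9 |
| | Rank ANCOVA | 85.6 | 86.1 | 87.8 | 89.1 |
| | ANCOVA | 83.2 | 84.2 | 86.4 | 88.1 |
| Strong skew | Mann-Whitney | 95.1 | 94.6 | 93.7 | 91.5 |
| | Rank ANCOVA | 94.8 | 95.3 | 95.5 | 95.6 |
| | ANCOVA | 87.0 | 88.8 | 90.0 | 91.8 |

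- Rank ANCOVA against Mann-Whitney, r = 0.2 to 0.4: gains from 0.7 points (80.4 − 79.7) to 5.6 points (85.3 − 79.7).
- At r = 0: losses of 0.8, 0.6 and 0.3 points.
- Plain ANCOVA against Mann-Whitney under strong skew: 94.6 − 88.8 = 5.8 points lost at r = 0.2 and 95.1 − 87.0 = 8.1 at r = 0.
- If the stratum shifts pain by an assumed 1 point, rank ANCOVA gains 2.1 to 8.2 points for r = 0.2 to 0.4.
- Type I error of rank ANCOVA was 4.8-5.2% over 24 null scenarios. Monte Carlo 95% error is about 0.6 points near 80% power, so the smallest gains and the r = 0 losses are close to simulation noise.

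**The case against.** The strongest reply is that the gain depends on a correlation the documents do not supply. At r = 0.2 it is only 0.7 to 1.0 point with a non-prognostic stratum, and at r = 0 it is slightly negative. The larger range also needs an assumed stratum effect. Under skew, which the plan expects, Mann-Whitney already has 84-95% power in these runs. All of this stands: the change needs no new data, but a gain is not assured.

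It is also fair to say that choosing rank ANCOVA over plain ANCOVA is partly preference. Every ANCOVA power in the table is at least 80.8%, so plain ANCOVA fixed in advance is acceptable. The case for ranks is the expected non-normality. Taking the test from ranks and the estimate from ANCOVA brings its own difficulty: in a check at 27 per arm the two disagreed on significance in about 3-6% of trials, so a rule is needed.

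Three stronger readings are tempting, and the documents do not support them.
- A reader might infer that the unadjusted comparison is biased or invalid. It is not; randomization protects it.
- A reader might infer that the trial is undersized. With 25 evaluable per arm and normal data, Mann-Whitney has about 78.9% power (large-sample efficiency 0.955), so adjustment there would partly recover a small shortfall. But the plan's 25 reproduces for a comparison of means, and 30 are enrolled per arm.
- A reader might infer that the analysis will be selected on the result. The text permits that reading but also permits baseline imbalance, so this is an ambiguity and not an established fault. For the same reason it would be too weak to say that precision alone is at stake.

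**Conclusion.** The point holds as a worthwhile improvement; it does not show an error that undermines the trial. Baseline NRS enters no between-arm comparison, and the stratum is adjusted for only on two undefined conditions. The main loss is precision: about 2 to 6 points of power in closed form (82.2% to 83.7-88.2%) and a CI half-width of 1.25-1.34 in place of 1.37. This rests on difference 2, SD 2.5, 27 per arm and an assumed r of 0.2 to 0.4. On the bounded scale, rank ANCOVA gains roughly 0.6 to 5.6 points over Mann-Whitney for the same r and costs about 0.3 to 0.8 at r = 0, both with a non-prognostic stratum. Whatever r proves to be, fixing one analysis in advance removes the possibility that the method is chosen after seeing the data.

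**What to change.** In section 3.8, delete the two-part trigger and pre-specify one primary between-arm analysis of NRS:

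- The model always includes treatment, the baseline value of the same NRS item, and the pain-location stratum as randomized.
- Rank ANCOVA is the primary test. Plain ANCOVA is an acceptable alternative if fixed in advance, accepting its possible loss under strong skew.
- The ANCOVA adjusted mean difference with 95% CI is reported as the effect estimate, on the scale used for sizing.
- The rank test governs the conclusion if the two disagree.
- The unadjusted Mann-Whitney test is kept as supporting.

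The same paragraph should name the NRS item (worst or mean), define the pain-location strata, and reconcile the primary time point between Appendix II (4 weeks) and section 1.3 (4 and 8 weeks). Without these the analysis is still not fully fixed.

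The cost is one paragraph. Baseline NRS is already collected and pain location is needed to randomize. The model spends one degree of freedom on baseline and one fewer than the number of strata.

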c. *Long Dorsal Sacroiliac Ligament (LDL) palpation test*: The subject lies on her side with slight flexion in both hip and knee joints. Specifically, the LDL is palpated directly caudomedially from the posterior iliac spine to the lateral dorsal border of the sacrum if palpation causes pain that persists five seconds after removal of the examiner's hand, it is recorded as pain. If the pain disappears within five seconds, it is recorded as tenderness. When the identical pain is felt directly in the vicinity, but outside the borders of the ligament, the test is not deemed as positive.

d. *Pubic Symphysis palpation test*: Examiners will palpate the subject's pubic symphysis joint while the patient is lying supine for tenderness. If palpation causes pain that persists five seconds after removal of the examiner's hand, it is recorded as pain. If the pain disappears within five seconds, it is recorded as tenderness.

e. *Modified Trendelenburg's test*: The standing woman stands on one leg and flexes the other at 90° (hip and knee). The test is considered positive if pain is experienced in the symphysis.

f. *Active Straight Leg Raise (ASLR) test*: performed with the patient supine with straight legs extended on the table 20 cm apart. The patient raises each leg one at a time 20 cm above the table without bending the knee. A) The test is positive when the patient describes a heaviness or difficulty in performing the task. B) In the second part of the maneuver, posterior

compression is applied and the patient is then asked to actively perform a straight leg raise. If there is greater ease in lifting the leg this is considered a positive test. The patient will be asked to score impairment (scoring inadequacy to raise the legs but not pain) on a 6-point scale: not difficult at all = 0, minimally difficult = 1, somewhat difficult = 2, fairly difficult = 3, very difficult = 4, unable to do = 5, the scores of both sides will be added so that the summed score can range from 0-10. Impairment is considered severe if the summed bilateral score is at least 4.

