Personal Health Information to be collected The personal health information (PHI) items that will be collected during pregnancy will include: name, phone number; date of birth; BMI; height; age; race; education level; income level; number of previous pregnancies; number of previous deliveries; types of previous deliveries, past abdominal surgeries if any, current medications; history of other pain diagnoses, history of depression; history of neurological disease; history of anxiety; history of sexual abuse; previous low back injury; previous low back or pelvic pain; history of smoking; history of infertility; history of urinary or fecal incontinence; history of interstitial cystitis; history of arthritic conditions (osteoarthritis, rheumatoid arthritis, lupus); body parts affected by arthritic conditions; diabetes (Type I, Type II, gestational); gestational week of current pregnancy; due date of current pregnancy; number of babies expected; trimester/gestational week of onset of low back and/or pelvic pain (if applicable); current pregnancy complications; occurrence of miscarriage; activity and exercise types and levels during pregnancy; activity level restrictions; and duration for any previous physical therapy; previous home exercise program; and physical therapy descriptions and reasons for initiating therapy after enrollment in the study. Social history including marital status, support at home, and type of occupation will be documented.

3.1 Eligibility criteria:

- English speaking pregnant women presenting in their second or third trimester with posterior PGP. Trimester will be determined from date of last menses or ultrasound date.

- Women who have failed physical therapy for pain management (physical therapy, chiropractic management, aquatic therapy)
- Pain NRS on average of greater than or equal to 5/10 at Visit 1
- Pain must be between the upper level of the iliac crests and the gluteal folds in conjunction with or separately from pain in the pubic symphysis and influenced by position and locomotion
- 2/4 positive physical examination tests on the symptomatic side including the P4 test, the LDL test, pubic symphysis palpation and the ASLR

3.2 Exclusion criteria:

- Non-English speaking pregnant women <21 or >50 years old
- Women presenting with PGP in the first trimester (<13 weeks gestation)
- Women with pubic symphysis (anterior) pain alone
- Women who have not yet received some form of physical therapy for their pain

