3.7 Sample size (Refer to Appendix III for calculations)

Protocol Version 4 – 03-06-2015

Sample size calculations are based on a 2-sided type I error rate of .05 and 80 % power. An additional 10% is added to account for loss to follow-up and for premature deliveries. Non-compliance is expected to be minimal given the short duration of the study medication intervention. The variance estimates are obtained from a previously reported RCT in pregnancy related PGP by Bastiaenen¹⁶. Approximately 50 participants will be needed to detect 2-point NRS effect size for 25 (exp) compared to 25 (control).

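### The between-arm comparison of the physical-examination tests ignores each woman's baseline result on the same test, at a modest cost in precision

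*Combined protocol and SAP*

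**What the plan says.** Section 1.2 asks, as a secondary question, whether the steroid injection improves the physical examination, and lists six tests: Patrick's Faber, P4, long dorsal ligament palpation, pubic symphysis palpation, modified Trendelenburg and ASLR. Section 3 has each maneuver recorded as positive or negative. The examination is done at visit 1 and repeated at 4 weeks, 8 weeks and 6 weeks postpartum (section 3 and Appendix I).

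For the between-arm comparison of these tests, section 3.8 has one sentence: "Additional secondary analyses will examine the impact of the treatment group assignment on physical examination tests using chi-square test of proportions". It names no covariate and no visit.

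Two other parts of 3.8 could have brought in the baseline result, but do not:

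- The Wilcoxon signed-rank analysis of change is within group, and follows the text on pain and disability.
- The multivariate analysis is conditional on approximate normality and on differences being found, which does not fit a binary outcome. Its covariate list contains no baseline test result.

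Section 3.1 sets the examination criterion for entry as "2/4 positive physical examination tests on the symptomatic side", drawn from P4, long dorsal ligament palpation, symphysis palpation and ASLR. Faber and modified Trendelenburg are not in that set. Section 3.5.2 stratifies randomization on pain location, not on examination results.

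**The concern.** A woman can satisfy the entry rule and still be negative at baseline on up to four of the six outcome tests: two of the four entry tests, plus Faber and Trendelenburg. On a test that is already negative she cannot improve. In an unadjusted comparison of follow-up proportions, such women dilute the contrast between arms. If one arm happens to start with more positives on a test, that excess also carries into the follow-up difference.

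The visit 1 result is probably a strong predictor of the later result on the same test, and it is available at no cost. With at most 30 women per arm, leaving it out can cost some power and makes the estimate more sensitive to chance imbalance. At stake is how well the trial can answer its secondary question on the examination. The primary pain comparison is not affected.

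**Working it through.** **1. The plan's own figure.** The documents state power only for the pain NRS: "a sample size of 50 (25 in each group) will give the study 80% power to identify a 2 point difference on the NRS". With a standard deviation of 25 mm, or 2.5 NRS points, Appendix II's formula gives n = (3.96 × 2.5 / 2)² = 24.5, so 25 per arm. The figure reproduces. No power, positivity rate or expected difference is given for any examination test.

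**2. Sample size used.** The plan enrols 30 per arm and expects 10% loss, so about 30 × 0.9 = 27 per arm are examined at follow-up.

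**3. Assumptions (none from the documents).**

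- Baseline positives still positive at follow-up: 75% control, 40% steroid.
- Baseline negatives positive at follow-up (control/steroid): 10%/5%, 20%/15% or 30%/20%.
- Positive at baseline: 50% to 90%.

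**4. One case by hand: 27 per arm, 60% positive at baseline, 10%/5%.**

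Unadjusted:
- Control: 0.6 × 0.75 + 0.4 × 0.10 = 0.49. Steroid: 0.6 × 0.40 + 0.4 × 0.05 = 0.26. Difference 0.23, against 0.35 among baseline positives.
- Null SE = √(2 × 0.375 × 0.625 / 27) = 0.132. Alternative SE = √((0.49 × 0.51 + 0.26 × 0.74) / 27) = 0.128.
- Power = Φ((0.23 − 1.96 × 0.132) / 0.128) ≈ 41%.

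Stratified (Cochran-Mantel-Haenszel), with 16.2 baseline positives and 10.8 negatives per arm:
- Expected numerator = 8.1 × 0.35 + 5.4 × 0.05 = 3.105.
- Null variance = (16.2² / 31.4) × 0.575 × 0.425 + (10.8² / 20.6) × 0.075 × 0.925 = 2.04 + 0.39 = 2.43, SD 1.56.
- Alternative variance = 8.1² × (0.1875 + 0.24) / 16.2 + 5.4² × (0.09 + 0.0475) / 10.8 = 1.73 + 0.37 = 2.10, SD 1.45.
- Power = Φ((3.105 − 1.96 × 1.56) / 1.45) ≈ 51%, a gain of about 10 points.

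**5. Simulation.** 30 per arm with each woman lost at random with probability 10%; 60,000 trials per setting; uncorrected chi-square versus Cochran-Mantel-Haenszel. Cells show power in % (unadjusted → stratified).

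| Positive at baseline | 10%/5% | 20%/15% | 30%/20% |
|---|---|---|---|
| 50% | 35 → 46 | 33 → 38 | 40 → 43 |
| 60% | 43 → 53 | 41 → 47 | 47 → 50 |
| 70% | 50 → 60 | 49 → 55 | 54 → 57 |
| 80% | 58 → 65 | 58 → 62 | 61 → 64 |
| 90% | 67 → 71 | 68 → 70 | 69 → 70 |

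From unrounded values, the gain is about 4-11 points in the first column, about 2.5-5 in the second and about 1.5-3 in the third.

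**6. Sensitivity to the exact arm size.** With exactly 25 per arm, the same assumptions give about −2 to +9 points. The negative values arise because the uncorrected chi-square rejects about 6% of the time under the null at that size, against about 5% for the stratified test. With exactly 27 per arm and 10%/5%, the gain is about 10-12 points at 50-80% positive. Letting arm sizes vary, as real losses would, smooths out these jumps.

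**7. Chance imbalance.** With 27 per arm and 60% positive at baseline, the arms differ by four or more baseline positives on a given test in about 33% of trials. Under the 10%/5% control rates, a gap of four shifts the expected follow-up difference by (4/27) × (0.75 − 0.10) = 0.096, or about 10 percentage points, with no treatment effect at all.

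**The case against.** The strongest reply is that nothing here is invalid. Randomization protects the unadjusted comparison, chance imbalance is already part of its error rate, the tests are labelled additional secondary analyses, and no power is claimed for them. That stands, and it is why the point is about efficiency only.

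The size can also be challenged. A reader might infer a fixed loss of 10-12 points of power. The documents do not support it, because they give no positivity rates and no link between baseline and follow-up. The figure appears at exactly 27 per arm when baseline negatives almost never turn positive. Later positivity is plausible as pregnancy advances, and the gain then shrinks to a few points.

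Two other inferences also fail:

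- That a test of proportions cannot suit ASLR because "the scores of both sides will be added so that the summed score can range from 0-10". Section 3 also defines a positive ASLR and a cut-off of at least 4 on the sum, so binary ASLR outcomes exist.
- That six tests at three visits give a 60% chance of a false positive (1 − 0.95¹⁸). This needs 18 independent tests, whereas these are overlapping tests repeated in the same women. Multiplicity is in any case no argument for baseline adjustment.

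Finally, the chi-square sentence does not say whether the proportion is of women positive or of women improved. Follow-up positivity is the natural reading, but it is an inference.

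**Conclusion.** The point holds at low severity. As written, 3.8 compares the binary examination outcomes without the visit 1 result on the same test, which is collected and is likely to be informative. The planned test remains broadly valid; it gives up some precision and lets chance baseline imbalance into the estimate.

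The power gain from stratifying is roughly nil to 11 points under the stated assumptions. It sits near the top when baseline negatives stay negative and baseline positivity is moderate. It is near nil when baseline negatives often turn positive or nearly all women start positive. All the rates behind this range are assumed. The documents support neither a single figure for the loss nor a claim that the planned test is wrong.

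**What to change.** In section 3.8, replace the chi-square sentence with a Cochran-Mantel-Haenszel test for each examination test, stratified on that test's visit 1 result, with a positive result defined the same way at both visits. Name 4 weeks as the main visit, which is the time point Appendix II uses for the drug effect, and name it by weeks because section 3 and Appendix I number the visits differently.

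The cost is one sentence, with no new data and no extra participants. The downside is that a sparse stratum, or one without events, contributes little or nothing, so the gain is negligible for a test on which almost every woman starts positive. Mantel-Haenszel is preferable to logistic regression in that situation.
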